10.1 Analysis sets

10.1.1 Full analysis set

The Full Analysis Set (FAS) comprises all patients who received at least one dose of the assigned combination of study drugs (ribociclib+ everolimus + exemestane).

10.1.2 Safety set

The Safety Set includes all patients who received at least one dose of any of the components from the investigational treatment, and have at least one valid post-baseline safety assessment. Investigational treatment/group refers to the triplet combination of ribociclib + everolimus + exemestane. The statement that a patient had no AEs (on the AE eCRF) constitutes a safety assessment.

10.1.3 DLT-determining analysis set

The DLT-determining set (DDS) includes all patients from the safety set in the dose escalation part who either completed a minimum exposure requirement and have sufficient safety evaluations in the first cycle or discontinued prematurely due to a dose limiting toxicity (DLT).

A patient is considered to have met the minimum exposure requirement if having received at least 75% of the planned combination doses (i.e. 21 out of 28 planned daily doses) for all compounds administered together (same day): ribociclib, everolimus and exemestane. The length of a cycle is 28 days.

Patients who do not experience a DLT during the first cycle will be considered to have sufficient safety evaluations if they have been observed for ≥ 28 days following the first dose, and are considered by both the Sponsor and Investigators to have enough safety data to conclude that a DLT did not occur.

10.1.4 Pharmacokinetic analysis set

The PK analysis set (PAS) consists of all patients who have at least one blood sample providing evaluable PK data. The PAS will be used for summaries of PK data (tables and figures) as well as for listings of derived parameters.

10.1.5 Per-protocol set

A subset of Full Analysis Set (FAS) excluding major protocol violations

10.2 Patient demographics/other baseline characteristics

Demographic and other baseline data including age, gender, height, weight, medical condition, and disease characteristics will be summarized descriptively. Treatments (study treatment, concomitant therapies, compliance).

10.3 Treatments (study treatment, concomitant therapies, compliance)

10.3.1 Study treatment

The actual dose and duration in days of ribociclib, everolimus and exemestane as well as the dose intensity (based on actual dose received and actual duration) and the relative dose intensity (computed as the ratio of dose intensity and planned dose intensity based on planned dose and planned duration), will be listed and summarized by means of descriptive statistics. The summary data will be presented for each treatment cycle individually, as well as for all study days as a single category. The total daily doses of ribociclib, everolimus and exemestane for each patient will be summarized using descriptive statistics (e.g. mean, median, maximum and minimum doses).

10.3.2 Concomitant therapies

Concomitant medications and significant non-drug therapies prior to and after the start of the study drug treatment will be listed by patient and summarized by ATC (Anatomical Therapeutic Chemical Classification System) term. These summaries will include medications starting on or after the start of study treatment or medications starting prior to the start of study treatment and continuing after the start of study treatment. Any prior concomitant medications or significant non-drug therapies starting and ending prior to the start of study treatment will be listed.

10.3.3 Compliance

Compliance to the protocol will be assessed by the number and proportion of patients with protocol deviations. These will be identified prior to database lock and will be listed and summarized by treatment group/study arm. Compliance to the study drug will be assessed by the number of dose reductions and dose interruptions).

10.4 Statistical hypothesis, model, and method of analysis

10.4.1 Study Design

This is a multi-center, open-label, Phase I/II study consisting of both Phase I dose escalation and dose de-escalation, and a Phase II. The dose escalation and de-escalation part of the trial will be conducted in men and postmenopausal women with HR+ HER2-negative advanced breast cancer that is endocrine resistant. Phase II will evaluate the antitumor activity of the combination of ribociclib +everolimus + exemestane combination in men and postmenopausal women with HR+HER2- advanced breast cancer that progressed on a CDK4/6 inhibitor.

10.4.2 Sample size and accrual

Phase I: In the phase I of the study, there will be 3-6 patients per dose level cohort (for a total of 3 cohorts). A RP2D will be based on safety profile of the dose escalation (cohort A&B) and the dose de-escalation (cohort C). RP2D will be defined as the optimal dose level at which 33% or less experience DLTs. Thus, including confirmation, at least 3-6 patients will be required for Phase I for each cohort.

Phase II:

The sample size is based on an exact test for single proportion to test the null hypothesis $H_0: p \leq 0.10$ where p is the clinical benefit rate in 24 weeks. If the true rate is $p \geq 30\%$, then with one-sided alpha level of 0.05% and a power of 80%, a minimum of approximately 60 (30 per group) evaluable patients are required for the study.

Including drop out rate of 10%, to get 60 evaluable patients, a total of approximately 66 patients (33 patients per group) will be enrolled for the phase 2 of the study for each group (group 1 and group 2). Thus, if fewer than 8 patients show clinical benefit at 24 weeks out of 33 patients within each group then the study will not show significant clinical benefit. Thus, approximately at least 66 patients (33 patients per group (group 1&2)) will be required to be enrolled for the Phase II of the study

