	
A minimum of approximately 60 evaluable patients (30 per group (group 1, and group 2) are required for Phase II of this study to evaluate clinical benefit rate at 24 weeks.
 
The sample size is based on an exact test for single proportion to test the null hypothesis $H_0: p \leq 0.10$, where p is the clinical benefit rate in 24 weeks. If the true rate is $p \geq 30\%$, then with one-sided alpha level of 0.05% and a power of 80%, a minimum of approximately 30 evaluable patients for each group are required for the study. Including dropout rate of 10%, to get at least 30 evaluable patients, a total of approximately 33 patients for each group (group 1 and group 2) will be enrolled.
 
If 8 or more patients show clinical benefit at 24 weeks then the null hypothesis will be rejected and significant clinical benefit will be demonstrated. (See Section 10)
 
Details of the statistical analysis and data reporting will be provided in the RAP.

--	---

1 Background

[figure not shown]

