10.5 Objectives

10.5.1 Primary objectives

Phase I: The primary objective of this dose escalation part of the study is to estimate the MTD(s) and/or RP2D of ribociclib in combination with everolimus and exemestane in postmenopausal women with HR+ HER2- advanced breast cancer.

Phase II: The primary objective is to evaluate efficacy measured by Clinical benefit rate (CBR) at 24 weeks for the triple combination of ribociclib + everolimus + exemestane among patients with HR+HER2- advanced breast cancer following the progression of CDK 4/6 inhibitors.

Demonstration of significant Clinical Benefit Rate (CBR) will be based on this study with at least an 80% power to test the null hypothesis that the clinical benefit rate in 24 weeks is at least 10% or less with an alternative hypothesis that this rate is above 10%.

The Clinical benefit rate will be presented together with an exact 95% Clopper-Pearson confidence interval. The null hypothesis will be rejected and successful clinical benefit will be demonstrated if the lower limit of the 95% confidence interval is greater than at least 0.10. Thus, if 8 or more patients show clinical benefit at 24 weeks then the null hypothesis will be rejected and significant clinical benefit will be demonstrated. Primary efficacy analysis will be performed on the FAS. For primary efficacy variable, the analysis time point is when all patients who are enrolled complete 24 weeks or discontinue from the study earlier. Phase 1 patients who had received the RP2D and are post CDK 4/6 completing 24 weeks or discontinue early will also be included in the final phase II analysis.

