2.1 Data analysis general information

Data will be analyzed by Novartis and/or the designated Contract Research Organization (CRO), according to the data analysis section of the study protocol. Any data analysis carried out independently by the investigator must be submitted to Novartis before publication or presentation. Data from all participating centers will be combined so that an adequate number of patients are available for analysis.

All statistical analyses will be performed using SAS® Version 9.4.

The planned statistical analysis is described in Section 10 of the protocol (Appendix 16.1.1 of the CSR). Data will be summarized with respect to demographic and baseline characteristics, efficacy and safety observations.

The study data will be analyzed and reported based on all patients' data up to the time when all patients have potentially completed at least six cycles of treatment or discontinued the study. Any additional data for patients continuing to receive study treatment past the data cutoff date for the primary CSR will be reported once all patients have discontinued the study or at the end of the study, whichever occurs first.

Data will be summarized and listed by dose groups. For safety end point, all patients will be analyzed for each phase and may be pooled for analysis. The efficacy data will be analyzed for Phase I and Phase II of this study separately.

Categorical data will be presented as frequencies and percentages. For continuous data, mean, standard deviation, median, 25th and 75th percentiles, minimum, and maximum will be presented.

Screen failure patients are those who signed the informed consent, but never started the study treatment for any reason. For these patients, the eCRF data collected, will not be included in any analysis, but will be reported in the CSR as separate listings.

The reason for discontinuation from study will be summarized and listed, along with dates of first and last study drug treatment, duration of exposure to study drug treatment and date of discontinuation for each patient. Other missing data will simply be noted as missing on appropriate tables/listings.

Unless otherwise specified, all statistical tests will be performed at a two-sided significance level of 0.05 and confidence intervals will be calculated with 95% confidence.

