3.5.2.2 Phase II

- Clinical Benefit Rate (CBR):

Clinical Benefit Rate (CBR) is defined as the proportion of patients with a complete response (CR), partial response (PR), stable disease (SD) or Non-CR Non-PD (NCRNPD) at 24 weeks as per RECIST V1.1. Thus, any instance of CR, PR, SD or NCRNPD in the first 24 weeks of the treatment, without having an instance of progressive disease (PD) will be accounted for, while calculating CBR. The instances of unconfirmed CR and/or PR will also be accounted for, while calculating CBR.

Demonstration of significant Clinical Benefit Rate (CBR) will be based on this study with at least an 80% power to test the null hypothesis that the clinical benefit rate in 24 weeks is at least 10% or less with an alternative hypothesis that this rate is above 10%.

All the other patients will be counted as not having clinical benefit.

The study is designed to test the following statistical hypothesis:

$$H_0 : \text{CBR} \leq 10\% \text{ vs. } H_1 : \text{CBR} > 10\%$$

The null hypothesis will be rejected and successful clinical benefit will be demonstrated if the lower limit of the 95% confidence interval is greater than at least 0.10. Thus, if 8 or more patients show clinical benefit at 24 weeks then the null hypothesis will be rejected and significant clinical benefit will be demonstrated.

To show significant clinical benefit, currently at least ≥ 8 patients will have to achieve CBR at 24 weeks. But if the number of patients enrolled in the study is higher than the planned number of 33 patients (approximately 44 to 46), then the requirement for the number of patients to have achieved CBR will also increase (up to ≥ 10 patients).

CBR will be summarized by frequency and percentage together with the 95% confidence intervals. An exact binomial confidence interval (implemented using SAS procedure FREQ with EXACT statement for one-way tables) will be calculated [Clopper & Pearson, 1934].

CBR will be calculated based on FAS; however, patients with only non-measurable disease at baseline will be included in the numerator if they achieved a complete response.

For primary efficacy variable, the analysis time point is when all patients who are enrolled complete 24 weeks or discontinue from the study earlier. Phase 1 patients who had received the RP2D and are post CDK 4/6 completing 24 weeks or discontinue early will also be included in the final phase II analysis.

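### The stated alpha, power and 30 per group do not fit the cut-off of 8, and at the 46 patients in Group 1 the protocol's count rule contradicts its own confidence-interval rule

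*Protocol*

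**What the plan says.** Protocol 10.4.2 bases Phase II on an exact single-proportion test in each group, with null rate at most 10% and alternative 30%: "one-sided alpha level of 0.05% and a power of 80%, a minimum of approximately 60 (30 per group) evaluable patients are required". The synopsis repeats this per group ("then with one-sided alpha level of 0.05% and a power of 80%, a minimum of approximately 30 evaluable patients for each group are required"), and SAP section 4 repeats it again. With 10% dropout, 33 per group are to be enrolled.

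The success rule appears in three forms:

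- Protocol 10.4.2 gives failure with a denominator: "if fewer than 8 patients show clinical benefit at 24 weeks out of 33 patients within each group".
- Protocol 10.5.1 gives an exact 95% Clopper-Pearson rule, with success "if the lower limit of the 95% confidence interval is greater than at least 0.10". It then infers a count without a denominator: "Thus, if 8 or more patients show clinical benefit at 24 weeks then the null hypothesis will be rejected".
- SAP 1.1 and 3.5.2.2 repeat the count of 8, then add that the requirement rises, up to 10, if about 44 to 46 patients are enrolled.

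SAP 2.1 says that, unless otherwise specified, "all statistical tests will be performed at a two-sided significance level of 0.05". SAP section 4 reports 46 patients recruited to Group 1 and 33 to Group 2. SAP section 5 lists no changes to the protocol's analyses.

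Protocol 10.5.1 and SAP 3.5.2.2 both add to the final Phase II analysis those Phase I patients who received the RP2D after a CDK4/6 inhibitor. SAP 2.1 says "The efficacy data will be analyzed for Phase I and Phase II of this study separately".

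**The concern.** The alpha, power, sample size and cut-off of an exact single-arm test determine one another, so they can be checked together. Here they do not match. A one-sided alpha of 0.05% is also far from the level that the 95% interval rule implies.

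The second problem affects the trial result. The protocol treats the count of 8 as equivalent to the interval rule, but the equivalence depends on N, and Group 1 has grown well past 33. If Group 1 had 8 or 9 patients with clinical benefit, the protocol's two statements of its own success rule would give opposite verdicts on the primary endpoint. The SAP addresses this only in part and does not record it as a departure from the protocol.

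**Working it through.** **Inputs.** p0 = 0.10, p1 = 0.30, n = 30 evaluable and 33 enrolled per group, cut-off 8 (Protocol 10.4.2). Exact 95% Clopper-Pearson lower limit above 0.10 (Protocol 10.5.1). Actual recruitment 46 and 33 (SAP section 4).

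**Formulas.** With X binomial(n, p) and cut-off c:

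- size = P(X ≥ c | n, 0.10)
- power = P(X ≥ c | n, 0.30)
- the lower limit L for x successes solves P(X ≥ x | n, L) = 0.025, so L > 0.10 exactly when P(X ≥ x | n, 0.10) < 0.025. The interval rule is therefore a one-sided 2.5% test.

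**Step 1: can the stated design be reproduced?**

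| Reading of alpha (one-sided) | n | Smallest valid c | Size | Power at 30% |
|---|---|---|---|---|
| 0.05%, as printed | 30 | 10 | 0.045% | 41.1% |
| 5% | 30 | 7 | 2.58% | 84.1% |
| 2.5% (interval rule) | 30 | 8 | 0.78% | 71.9% |
| 0.05%, as printed | 33 | 11 | 0.024% | 40.1% |
| 5% | 33 | 7 | 4.17% | 90.6% |
| 2.5% (interval rule) | 33 | 8 | 1.41% | 81.8% |

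No row with n=30 has both c=8 and 80% power. At the printed 0.05%, 80% power is first reached at n=62 (c=16, power 80.4%). A cut-off of 8 with at least 80% power appears only at n=33 and one-sided 2.5%. At 2.5% and c=8, power is 72% at n=30, 76% at 31, 79% at 32 and 82% at 33.

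The 82% assumes that all 33 patients have the 30% rate. If the 10% who drop out all counted as failures, the rate would be 0.9 × 0.30 = 0.27 and power at n=33 would be 70.2%. This is an assumption at the unfavourable end: under SAP 3.5.2.2 a patient with stable disease before dropping out and no recorded progression can count as a benefit.

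**Step 2: where does the count of 8 equal the interval rule?**

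| N | Minimum successes | Lower limit at that count, first and last N | Lower limit one success short, first N |
|---|---|---|---|
| 30–36 | 8 | 8/30: 0.1228; 8/36: 0.1012 | 7/30: 0.0993 |
| 37–43 | 9 | 9/37: 0.1177; 9/43: 0.1004 | 8/37: 0.0983 |
| 44–50 | 10 | 10/44: 0.1147; 10/50: 0.1003 | 9/44: 0.0980 |
| 51–57 | 11 | 11/51: 0.1129; 11/57: 0.1005 | 10/51: 0.0982 |

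**Step 3: Group 1 at N=46.**

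| Result | Lower limit | Size of that cut-off | Protocol count | Interval rule |
|---|---|---|---|---|
| 8/46 | 0.0782 | 8.4% | success | failure |
| 9/46 | 0.0936 | 3.6% | success | failure |
| 10/46 | 0.1095 | 1.4% (power 92.1%) | success | success |

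**Step 4: pooled Phase I patients.** The number is not given, and Protocol 5.1 does not require prior CDK4/6 exposure in Phase I, so the lower bound is 0. The upper bound is inferred from enrolment:

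- The Amendment 2 rationale reports 18 Phase I patients before cohort C, and the Amendment 3 text reports 25 in all. Cohort C is therefore 25 − 18 = 7.
- Cohorts A and B had 8 evaluable patients each (Protocol 1.2.5.1.2), leaving 18 − 16 = 2 unallocated. Cohort B, the Group 1 dose, is therefore about 8 to 10.
- Group 1 could reach N = 46 + 10 = 56. From N=51 (5 or more pooled), 11 successes are needed, above the SAP's ceiling of 10.
- Group 2 could reach N = 33 + 7 = 40. From N=37 (4 or more pooled), 9 successes are needed.

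**The case against.** The strongest reply is that 0.05% is an obvious misprint for 5% and that the substance is already covered. Read at 5%, 30 per group is adequate, with 84% power. Protocol 10.4.2 ties the 8 to 33 patients, where it is correct. The primary analysis uses the full analysis set, so the planned N is near 33 and power meets the stated 80%. Protocol 10.5.1 states the interval rule first and only infers the count from it. The SAP's bar of 10 is exactly the interval bar at 46, so it can be seen as applying the protocol's rule rather than changing it. The SAP's two-sided 0.05 yields to anything specified otherwise, and the sample-size text does specify a one-sided test. The pooling exposure depends on counts that no document gives, and a specific pooling provision can qualify a general statement about separate analysis.

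Much of this is fair. The SAP's 10 is right for N=44 to 50, the pooled numbers are a range, the general SAP level does not settle the matter, and the pooling wording is the weakest part of the concern.

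The core still stands. Correcting the misprint to 5% makes the cut-off 7 at both n=30 and n=33, so the 8 would then be wrong. It would also let 9/46 succeed on size (3.6%) while failing the interval rule. The 2.5% level follows from the interval rule alone. The SAP keeps the unconditional 8 beside its higher bar, gives no bar between 33 and about 44 or above 10, and the protocol contains no adjustment.

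**Conclusion.** The plan is wrong as written. The printed alpha cannot be right, and 80% power is not a property of 30 patients with a cut-off of 8: it is 72% there, and 82% at 33 analysed if all 33 share the 30% rate. For Group 1 at 46 patients, results of 8 and 9 pass the protocol's count and fail its interval rule. The count rule's type I error at that size is 8.4%, against 1.4% for a bar of 10.

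These figures rest on the exact binomial with the documents' 10% and 30%, and on all 46 recruited patients entering the full analysis set. The need for 11 in Group 1 or 9 in Group 2 is conditional on at least 5 or at least 4 Phase I patients being pooled, respectively.

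**What to change.** 1. State the one-sided alpha as 2.5% in Protocol 10.4.2, the synopsis and SAP section 4, to match the two-sided 95% Clopper-Pearson rule. If the sponsor did intend 5%, the interval rule and the cut-off must both change.
2. Restate the design as 33 analysed per group, success at 8 or more, size 1.4% and power 82% at a 30% rate. Note that power is 72% if only 30 are analysed.
3. In both documents, make a Clopper-Pearson lower limit above 0.10 on the actual analysed N, including any pooled Phase I patients, the only decision rule. Give the minimum successes: 8 for N=30–36, 9 for 37–43, 10 for 44–50 and 11 for 51–57. Delete the fixed count of 8 and the SAP's ceiling of 10.
4. Record the changed bar in SAP section 5. Cross-refer the pooling provision to the statement on separate analysis, state how many Phase I patients join each group, and report the Phase II-only result alongside. Whether pooled patients belong in the primary test remains the sponsor's choice.

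The cost is wording in two documents and one extra table. The stated power at 30 per group becomes less favourable.

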10.5 Objectives

10.5.1 Primary objectives

Phase I: The primary objective of this dose escalation part of the study is to estimate the MTD(s) and/or RP2D of ribociclib in combination with everolimus and exemestane in postmenopausal women with HR+ HER2- advanced breast cancer.

Phase II: The primary objective is to evaluate efficacy measured by Clinical benefit rate (CBR) at 24 weeks for the triple combination of ribociclib + everolimus + exemestane among patients with HR+HER2- advanced breast cancer following the progression of CDK 4/6 inhibitors.

Demonstration of significant Clinical Benefit Rate (CBR) will be based on this study with at least an 80% power to test the null hypothesis that the clinical benefit rate in 24 weeks is at least 10% or less with an alternative hypothesis that this rate is above 10%.

The Clinical benefit rate will be presented together with an exact 95% Clopper-Pearson confidence interval. The null hypothesis will be rejected and successful clinical benefit will be demonstrated if the lower limit of the 95% confidence interval is greater than at least 0.10. Thus, if 8 or more patients show clinical benefit at 24 weeks then the null hypothesis will be rejected and significant clinical benefit will be demonstrated. Primary efficacy analysis will be performed on the FAS. For primary efficacy variable, the analysis time point is when all patients who are enrolled complete 24 weeks or discontinue from the study earlier. Phase 1 patients who had received the RP2D and are post CDK 4/6 completing 24 weeks or discontinue early will also be included in the final phase II analysis.

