The decisions on new dose combinations are made by the Investigators and Novartis study personnel and will be based upon a synthesis of the recommendations made by the independent data monitoring committee (IDMC), patient tolerability and safety, PK and efficacy information available at the time of the decision. The discussion and decisions will be documented in the dose escalation meeting minutes.

The dose escalation part of this study will also assess the PK of everolimus and ribociclib in HR+ HER2-negative advanced breast cancer patients receiving the triplet combination (ribociclib + everolimus + exemestane) with continuous dosing and will compare the findings with historical data for the approved combination of everolimus + exemestane as well as the data from the ongoing CLEE011X2106 study. This comparison will be done in order to determine the optimal dosing of the triplet combination when all drugs are dosed continuously. Each cycle was determined to be 28 days. In the initial cohort(s) of subjects, if therapy is well tolerated after two cycles and have no evidence of grade 3 or 4 clinically significant AEs, subjects may undergo intra-patient dose escalation(s) to ensure that they receive a therapeutic dose of everolimus and ribociclib. See [Section 6.2](#) for details on starting dose and escalation guidelines.

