***Note: There are no restrictions as to which endocrine therapy patients received as their last line of therapy just prior to randomization.**

8. Patients who received up 3 lines of therapy for advanced breast cancer are allowed. This includes a maximum of 1 line of chemotherapy and a maximum of 3 lines of endocrine therapy in the advanced setting so long as the patient has not received more than a total of 3 lines of therapy. Patients must have recovered to grade 1 or better from any adverse events (except alopecia and/or neuropathy) related to previous therapy prior to starting study treatment.

Note: If patient relapsed with documented evidence of progression on/or within 12 months from completion of adjuvant endocrine therapy, then this is considered one line of therapy.

9. Patients previously treated on any CDK 4/6 inhibitor (i.e. ribociclib, abemaciclib OR palbociclib) must have:
 - Remained on treatment for ≥ 4 months for advanced breast cancer or metastatic disease prior to progression, AND
 - Progressed on, or within 30 days following the discontinuation of a CDK 4/6 inhibitor.

Phase II Only:

- Patients must have progressed on only one CDK 4/6 inhibitor. A CDK 4/6 inhibitor must have been the last treatment regimen prior to starting study treatment.

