Any additional data for patients continuing to receive study treatment past the data cutoff date for the primary Clinical Study Report will be reported once all patients have discontinued the study or at the end of the study, whichever occurs first.

Data will be summarized and listed by study group.

For safety endpoint, all patients will be analyzed for each phase and may be pooled for analysis. The efficacy data that will be analyzed for Phase I and Phase II of this study separately

Categorical data will be presented as frequencies and percentages. For continuous data, mean, standard deviation, median, 25th and 75th percentiles, minimum, and maximum will be presented.

Screen failure patients are those who signed the informed consent, but never started the study treatment for any reason. For these patients, the eCRF data collected, will not be included in any analysis, but will be reported in the CSR as separate listings.

The reason for discontinuation from study will be summarized and listed, along with dates of first and last study drug treatment, duration of exposure to study drug treatment and date of discontinuation for each patient. Other missing data will simply be noted as missing on appropriate tables/listings.

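### The primary CBR set is contradictory: Phase I patients are pooled into Phase II in one place and kept separate in another, and the pooling clause omits the last-regimen rule and does not require the RP2D as starting dose

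*Protocol*

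**What the plan says.** Within the primary-endpoint text, Protocol 10.5.1 says of the final Phase II analysis: "Phase 1 patients who had received the RP2D and are post CDK 4/6 completing 24 weeks or discontinue early will also be included". SAP 3.5.2.2 repeats the sentence. The opening text of Protocol Section 10 says: "The efficacy data that will be analyzed for Phase I and Phase II of this study separately". SAP 2.1 agrees: "The efficacy data will be analyzed for Phase I and Phase II of this study separately".

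Entry rules: inclusion criterion 9 (Protocol 5.2) requires any patient previously treated with a CDK4/6 inhibitor, in either phase, to have had at least 4 months of it and to have progressed on it or within 30 days of stopping. Exclusion criterion 8 bars progression on more than one such drug, again in both phases. One rule is for Phase II only: "A CDK 4/6 inhibitor must have been the last treatment regimen prior to starting study treatment".

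Dose: cohort A started ribociclib at 250 mg. The Group 1 RP2D is 300 mg (cohort B) with everolimus 2.5 mg. The Group 2 RP2D is the cohort C starting combination. Protocol 2.1.1 says that in the initial cohort(s), after two well-tolerated cycles, "subjects may undergo intra-patient dose escalation(s) to ensure that they receive a therapeutic dose of everolimus and ribociclib".

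Success rule: the exact 95% lower limit must exceed 0.10, restated as 8 or more patients with benefit. The SAP raises the count to at most 10 for about 44 to 46 patients. SAP 3.5.4 lists no supportive analyses. The only repeats named in SAP 3.5.2.2 are by local assessment and in the per-protocol set. SAP Section 5 records no change from the protocol.

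**The concern.** Two analysts could each follow the text and report different primary results, one with and one without the Phase I patients. No Phase II-only analysis is planned that would show the difference.

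The clause also does not reproduce the Phase II conditions. A Phase I patient who took another therapy between the CDK4/6 inhibitor and study entry fits its wording but could not have entered Phase II. A cohort A patient raised to 300 mg after two cycles also fits it, but only because she was still on treatment at about week 8. That is selection on something close to the endpoint.

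The fixed success counts were not written for a pooled N, so the count rule and the interval rule can disagree.

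**Working it through.** **Inputs.** Null rate 10% and alternative 30% (Protocol 10.4.2, 10.5.1). Phase II recruitment 46 in Group 1 and 33 in Group 2 (SAP Section 4). Cohort B: 8 evaluable patients (Protocol 1.2.5.1.2). Cohort C: about 7, taken as 25 Phase I patients in the Amendment 3 summary minus 18 in the Amendment 2 summary. How many of these were post-CDK4/6 is not stated, so the number added is 0 to 8 for Group 1 and 0 to 7 for Group 2. The results below use the upper ends unless stated.

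**The plan's own rule.** For X ~ Bin(33, p), P(X ≥ 8) is 0.0141 at p = 0.10 and 0.818 at p = 0.30. The Clopper-Pearson lower limit for 8/33 is 0.111. The 8-of-33 rule therefore reproduces with about 80% power and a 2.5% one-sided tail. (The printed one-sided alpha of 0.05% does not reproduce it; that is a separate matter.) For 10/46 the lower limit is 0.1095, the null tail 0.0140 and the power 0.920.

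**Effect on the verdict.** The lower limit is the 2.5% quantile of Beta(r, n − r + 1) and passes if above 0.10.

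| | Phase II only | Pooled |
|---|---|---|
| Group 2, fail to pass | 7/33: 0.0898 | 9/40: 0.1084 |
| Group 2, pass to fail | 8/33: 0.1109 | 8/40: 0.0905 |
| Group 1, fail to pass | 9/46: 0.0936 | 11/54: 0.1063 |
| Group 1, pass to fail | 10/46: 0.1095 | 10/54: 0.0925 |

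**Type I error.** Phase II patients are at 10% and the added patients at rate q. The cut-off is the smallest count that passes the interval rule at the pooled N.

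- Group 2, P(Bin(33, 0.10) + Bin(7, q) ≥ 9): 1.55% at q = 10%, 3.8% at 20%, 7.7% at 30%.
- Group 1, P(Bin(46, 0.10) + Bin(8, q) ≥ 11): 1.66%, 4.0% and 7.9%.
- Smaller additions, same three values of q. 33 + 3 (cut-off 8): 2.4%, 3.5%, 5.0%. 33 + 4 (cut-off 9): 0.9%, 1.7%, 2.8%. 46 + 4 (cut-off 10): 2.5%, 3.8%, 5.6%.

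**Count rule against interval rule.** 8/36 has lower limit 0.1012 and 8/37 has 0.0983, so a count of 8 fails the interval rule from n = 37. 10/50 has 0.1003 and 10/51 has 0.0982, so a count of 10 fails from n = 51. If the count were followed anyway at the pooled N, the null tail would be 4.2% for 8/40 and 4.0% for 10/54.

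**Escalated patients.** Assume exponential time to progression with S(24 weeks) = p. Then S(24)/S(8) = p^(2/3). A true 24-week rate of 10% becomes 0.10^(2/3) = 21.5% among patients progression-free at week 8, and 20% becomes 34.2%.

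**The case against.** Pooling run-in patients treated at the RP2D is accepted practice. Here it is prespecified in the same words in both documents, and it counts early discontinuers, so it is not a completers' analysis. The statements about separate analysis are general, and Phase I does have its own efficacy section in the SAP. These points stand, and they are why pooling need not be abandoned. They do not remove the conflict, because nothing says which statement prevails.

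The RP2D may also be read as the assigned dose, since the full analysis set is defined by the assigned combination. Protocol 2.1.1 refers to Section 6.2 for escalation guidance, but 6.2 contains no intra-patient procedure. The condition for escalation is tolerability, and the first scan is due at week 8 ± 1, so escalation could come before it. The 21.5% is therefore an illustration under a model.

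Several stronger readings are tempting, but the documents do not support them:

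- That the pooled patients bypass the Phase II entry rules in general. Only the last-regimen rule is lost; the other CDK4/6 rules apply to both phases, and CDK4/6-naive patients are not pooled.
- That the primary objective itself specifies last regimen and fixed dose. Protocol 3.2 and 10.5.1 say only that patients had progressed on a CDK4/6 inhibitor.
- That choosing the dose on efficacy biased the CBR. Protocol 2.1.1 lists "patient tolerability and safety, PK and efficacy information available at the time of the decision" among the inputs, but Protocol 6.2.1 and 10.4.2 rest the RP2D on dose-limiting toxicity and tolerability. No such bias is shown.
- That pooling favours success. If everyone is at 10%, the chance that pooling turns a fail into a pass is 0.62% and the reverse 0.48% (33 + 7), or 0.65% and 0.40% (46 + 8).

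**Conclusion.** The point holds as a contradiction over who is in the primary analysis, together with a pooling clause that is too loose on two counts: last regimen and starting dose. At the upper assumed counts (7 and 8 added), pooling can reverse either group's verdict in either direction. Type I error stays at 1.6–1.7% if the added patients share the null rate and reaches 3.8–7.9% if their true rate is 20–30%, against 2.5% nominal. With fewer patients added the effect is mostly smaller, and with none it vanishes.

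The 20–30% rates are assumptions; the documents give no CBR for the patients who would be pooled. Nor do they show that any patient was escalated or had intervening therapy, so inflation is possible under the wording but not demonstrated. The mismatch between the written counts and the interval rule needs no assumption about rates: it follows once the analysed N reaches 37 with a cut-off of 8, or 51 with a cut-off of 10.

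**What to change.** Reconcile the opening of Protocol Section 10 and SAP 2.1 with Protocol 10.5.1 and SAP 3.5.2.2, and fix one primary set before database lock. Either of two versions would do:

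1. **Phase II only.** The primary set is Phase II-enrolled FAS patients, by group, and the pooled result is supportive. With 46 and 33 recruited against 33 planned per group, no planned size is lost; power at 30% is 0.92 (at least 10/46) and 0.82 (at least 8/33).
2. **Restricted pooling.** Admit only Phase I patients assigned to the RP2D from the first dose who met every Phase II criterion, including the last-regimen rule. Let the exact interval at the actual N govern in place of a fixed count, and report the Phase II-only result as a sensitivity analysis.

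In either case, report how many Phase I patients enter any pooled analysis, by group. The cost is a change of wording in both documents and a slightly smaller denominator than the present clause would give.
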